We will record demographics, general medical information, questionnaires, and medication usage (including frequency and doses) using the REDCap database designed by the researcher and hosted by the Cleveland Clinic. REDCap (Research Electronic Data Capture) is a secure, web- based application designed to support data capture for research studies, providing 1) an intuitive interface for validated data entry; 2) audit trails for tracking data manipulation and export procedures; 3) automated export procedures for seamless data downloads to common statistical packages; and 4) procedures for importing data from external sources. The database will be reviewed by a statistician prior to data collection. Only the PI and research co-investigators will have access to the stored information. Only the PI, co-PI's and those responsible for analysis will have rights to export identifiable data. The subject's personal health information will be stored in the secure research database and only limited research personnel have access to this database. Great care will be taken to ensure that confidential health information is stored securely and accessible only to the PI and co-investigators.

RANDOMIZATION

In order to minimize bias in the study, we will stratify subjects based on presence or absence of levator spasm.

STATISTICAL METHODS

Numerical values will summarized by mean and standard deviation when they appear to have a normal distribution; otherwise, they will be summarized by median and interquartile range. Categorical values will be summarized by frequency and percentage. Univariable comparisons between groups will be made using two sample t-tests, Wilcoxon rank sum tests, or Chi-square tests, depending on the level of measurement and data distributions.

STUDY AIM ANALYSIS

- 1. Change in pain score from baseline to 12 weeks will be compared using a two-sample t-test. A multivariable linear regression model may be considered if baseline differences between groups are observed.
- 2. Changes in SF-36 subscores from baseline to 12 weeks will be compared using Wilcoxon rank sum tests.
- 3. Changes in FSFI subscales from baseline to 12 weeks will be compared using Wilcoxon rank

sum tests.

4. Frequency of medication from baseline to 12 weeks may be compared using a poison regression model. Dose of medication will be compared using a Wilcoxon's rank sum test.

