Additional analyses using longitudinal methods, including linear mixed effects models and generalized linear mixed effects models, may be used in subsequent analyses to explore the length of time that elapses before the treatment benefit is observed. In all analyses, statistical significance will be determined by a p-value less than or equal to 0.05. Analyses will be performed using R version 3.1.1 (2014-07-10) statistical software (or a later version).

Two interim analyses are planned for this study, to be conducted at 25% recruitment and 50% recruitment. These analyses will be conducted using significance levels of 0.017 and 0.033, respectively. A stopping rule will be applied of any statistically significant increase in pain from baseline as reported on the visual analog scale. The percentage of patients dropping out from the study will also be monitored, with a significantly higher percentage of electrical stimulation patients dropping out being considered a potential safety issue.

POWER ANALYSIS

The researcher currently estimates typical reported pain from this population of patients to be between 8 and 9 on a 10 point scale. A clinically meaningful improvement would be a 30% reduction in reported pain. For the purposes of the power analysis, we assume that the placebo effect of the sham treatment may reduce reported pain by 10%. We assign the mean baseline pain value of 8.5 to each group with a standard deviation of 1. A 30% reduction in pain corresponds to a mean score of 5.9 and a 10% reduction of pain corresponds to a mean score of 7.7. The sample size analysis is based on a two-sample, two-sided t-test with a significance level of 0.05 and 80% power. The sample size analysis indicates that for a 30% reduction in pain, a total sample size of 46 is required to provide 80% power for the study. To reduce the impact of attrition on the final study results, we plan on recruiting 10% more than the minimum sample size. This amounts to a total of 52 patients (26 patients per arm).

ADVERSE EVENTS AND DATA SAFETY MONITOR

Patients are asked to record any side effects, adverse effects and unanticipated problems daily. In Version 6 Aug 2015

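### The total of 46 does not follow from the printed planning inputs, which need 12 to 14 if the only stated SD is used, and the SD of the 12-week change is missing

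*Combined protocol and SAP*

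**What the plan says.** All the planning figures are in the Power Analysis section of the combined protocol and SAP.

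- Baseline: "We assign the mean baseline pain value of 8.5 to each group with a standard deviation of 1". This is the only SD in the document.
- Follow-up: "A 30% reduction in pain corresponds to a mean score of 5.9 and a 10% reduction of pain corresponds to a mean score of 7.7". Of these reductions, the larger is the clinically meaningful improvement; the smaller is the assumed sham effect.
- Test: "The sample size analysis is based on a two-sample, two-sided t-test with a significance level of 0.05 and 80% power".
- Result: "a total sample size of 46 is required to provide 80% power for the study". Ten per cent is then added for attrition, giving 52, or 26 per arm.

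Under Study Aim Analysis, the primary comparison is defined on change: "Change in pain score from baseline to 12 weeks will be compared using a two-sample t-test". For the two interim looks, the Statistical Methods text adds: "These analyses will be conducted using significance levels of 0.017 and 0.033, respectively".

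**The concern.** The paragraph prints a difference, an SD, a significance level and a power, which is everything a two-sample t-test calculation takes. A difference of 1.7 to 1.8 points against an SD of 1 is very large in standardised terms and should need only a handful of patients per arm, so 46 looked too big by a factor of three or more. In addition, the only SD is attached to baseline pain, while the analysis is of change to 12 weeks, and the SD of that change is not given.

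The 46 is the sole basis for the planned recruitment of 52. If it cannot be reproduced, a reader or IRB cannot tell whether the trial plans to recruit over three times what its own paragraph requires, is sized as claimed, or falls short of 80% power.

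**Working it through.** **Inputs from the Power Analysis section.** Baseline mean 8.5; SD 1; reductions of 30% and 10%; two-sided alpha 0.05; power 80%; equal arms.

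**Difference between arms.**
- Unrounded: 8.5 × 0.70 = 5.95 and 8.5 × 0.90 = 7.65, a difference of 1.70.
- As printed: 7.7 − 5.9 = 1.8.

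**Method.** With n per arm, the t statistic has 2n − 2 degrees of freedom and noncentrality (difference / SD) × √(n/2). Power is the probability that it falls beyond the two-sided critical value. The required n is the smallest that reaches 80%.

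**Step 1: try to reproduce 46 from the printed inputs (SD 1).**

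| Difference | Power, 6 per arm | Power, 7 per arm | Total needed | Power, 23 per arm |
|---|---|---|---|---|
| 1.8 | 80.2% | 87.0% | 12 | >99.9% |
| 1.7 | 75.6% | 83.1% | 14 | >99.9% |

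The stated 46 is not reproduced. It is 46/14 = 3.3 to 46/12 = 3.8 times the computed total. The rounding of the means moves the answer only between 12 and 14.

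**Step 2: look for an explanation inside the document.**
- Interim significance levels: at 0.017 the total is 18 for either difference; at 0.033 it is 16 (1.7 points) or 14 (1.8 points).
- Attrition: it is added after the 46. That step is consistent, since 46/0.9 = 51.1 and 46 × 1.1 = 50.6, each giving 52 when rounded up to equal arms.
- Change score with SD 1 at both visits (an assumption): the SD of change is √(2(1 − ρ)). With ρ = 0 this is 1.41 and the total is 24 for 1.7 points (22 for 1.8). With ρ = 0.5 it is 1 and the total is 14 (12). Any non-negative correlation gives at most 24.

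**Step 3: find what would give 46.** Twenty-three per arm is the smallest size reaching 80% when the standardised difference is between about 0.845 and 0.864. For 1.7 points that means an SD of 1.97 to 2.01. Three input pairs with a ratio of 0.85, each giving 80.5% power, are:
- 1.7 points with SD 2.0
- 0.85 points with SD 1
- 2.55 points with SD 3

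None of these is printed, and nothing shows which, if any, was used.

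An SD of change of 2.0 is compatible with a baseline SD of 1 if the 12-week SD is larger. As an assumed example, a 12-week SD of 2.06 and ρ = 0.3 give √(1² + 2.06² − 2 × 0.3 × 1 × 2.06) = √4.008 = 2.00.

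**Step 4: what the missing SD does to power (difference 1.7; every SD of change is assumed).**

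| SD of change | Total needed for 80% | Power, 23 per arm | Power, 26 per arm (no dropout) |
|---|---|---|---|
| 1.0 | 14 | >99.9% | >99.9% |
| 1.5 | 28 | 96.4% | 98.0% |
| 2.0 | 46 | 80.5% | 85.2% |
| 2.25 | 58 | 70.7% | 76.2% |
| 2.5 | 70 | 61.6% | 67.2% |
| 3.0 | 100 | 46.8% | 51.8% |

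With 23 per arm, power drops below 80% once the SD of change exceeds about 2.01. With the rounded difference of 1.8 the threshold is about 2.13.

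**The case against.** The strongest reply is that the SD of 1 describes baseline pain only. The test is on change, so the sponsor may have used a larger SD of change, and 46 may be right but undocumented. On that reading, 12 to 14 holds only if SD 1 is taken as the SD for the test. This is fair and sets the limit of the conclusion: an arithmetic slip is not proved. It does not rescue the paragraph, because the SD that the test needs is then absent.

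A second reply is that no harm is shown. On the only printed SD, 46 is ample; underpowering appears only at SDs of change that the document never mentions; and full retention of 26 per arm would raise power somewhat. All of that stands, and the lower power figures are scenarios, not estimates. The trial is also presented as a step towards a larger multi-centre study. Even so, the plan makes a specific claim of 80% power at 46, and that claim conflicts with the inputs given for it.

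**Conclusion.** The concern holds. Using the only SD printed, the stated test needs 12 to 14 patients in total, not 46, and 23 per arm would give more than 99.9% power. The interim significance levels, the attrition allowance and a change score with SD 1 at both visits and non-negative correlation do not close the gap. Reaching 46 takes a standardised difference of about 0.85, and therefore at least one input that the document does not state.

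The conclusion rests on equal arms and the t-test as specified. It does not say that the baseline SD of 1 is wrong, that 46 is too many, or that the trial is underpowered. It says that 46 cannot be derived from what is printed and that the deciding quantity, the SD of the 12-week change, is missing. This must be fixed because no other justification of the sample size is given.

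**What to change.** Recover the original calculation and rewrite the Power Analysis paragraph with the inputs actually used. It should state:

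- a two-sided two-sample t-test at 0.05 on change in pain score from baseline to 12 weeks;
- the expected difference, which is 1.7 points if the 30% and 10% reductions are kept (8.5 to 5.95 against 8.5 to 7.65);
- the SD of change used, with its source;
- the power that 46 evaluable patients (23 per arm, 52 to be recruited) give under those inputs.

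If the calculation cannot be recovered, say so, justify an SD of change from a named source, and report power over a range such as 1.5 to 2.5. Inputs should not be chosen merely because they return 46. If the justified SD gives less than 80% power, the paragraph should state that power.

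The cost is one reworded paragraph, plus the effort of finding the original calculation or a source for the SD. The endpoint and the test do not change. The stated power may turn out less favourable than 80%.
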